## Medications

*Treatment with PTH:* Subjects will be randomized at the beginning of the first inpatient admission and will remain on this dose schedule until the second admission (3 months later). Synthetic human parathyroid hormone 1-34 will begin on day 3 of the first admission and will be given as a twice daily subcutaneous injection as a divided dose at 0800 h and 2000 h or via a pump. PTH is prepared by the Clinical Center PDS in two vial strengths: 50 mcg/mL and 200 mcg/mL. The initial PTH dose will be 0.5 µg/kg/day for twice daily dosing and 0.2 µg/kg/day for pump therapy. The total daily dose will be adjusted by approximately twenty percent increments for mild hypo- or hypercalcemia. For severe hypocalcemia, the dose will be adjusted by larger increments and calcium supplements may be added. For severe hypercalcemia, the patient will stop the drug for at least one day and then resume treatment at a lower dose. For further details of pump therapy, see appendix 2

## Criteria for Withdrawal of Subjects from the Study

Voluntary withdrawal from the protocol is always an option for the research participants. The following conditions will require the withdrawal of a subject from the study:

Pregnancy; new onset illness that requires chronic use of a medication that adversely effects the kidney or bone such as glucocorticoids, significant deterioration in metabolic control on PTH; severe chronic muscle or bone pain or other unexpected new onset chronic medical condition that can not be explained and may be related to PTH therapy such as weight loss. Subjects who develop tumors will be withdrawn from the study.

## Protocol Stopping Criteria

(1) Blood mineral levels cannot be maintained in the normal or near normal range. (2) Persistent mistakes by subject in pump use suggesting an inability to understand how to change doses. Protocol withdrawal would be a last resort after repeated training sessions during the Clinical Center admission. (3) Persistent mistakes in drawing up the PTH dose from vial demonstrating an inability to self inject. (4) An episode of severe hyper- or hypocalcemia (requiring medical intervention) that cannot be explained (noncompliance or dose error) and remedied with usual adjustment in dose.

**Sample Size Justification:** Our power estimates were based on the ability to observe a significant increase in serum levels of each outcome at the 6 h time point, when PTH is known to peak after a subcutaneous injection. Based on our previous data, serum calcium levels exhibited the most variability and thus sample size calculations are based on this variable. Studies investigating the impact of subcutaneous delivery of hPTH 1-34 on serum calcium levels demonstrated an increase in serum calcium from 2.0 +/- 0.05 mmol/L at baseline to 2.3 +/- 0.10 mmol/L at 6 h. With a standard deviation of 0.10 mmol/L, a two-sided significance level of 0.05 a sample size of 8 subjects will provide 93% power to detect an increase in serum calcium of 0.10 mmol/L.

We will initially enroll 8 adults with chronic surgically induced hypoparathyroidism and study them in a randomized controlled study on both BID injections and PTH infusion pump therapy. We will subsequently enroll 16 children with more severe forms of hypoparathyroidism: calcium receptor mutation or autoimmune polyglandular failure.

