### 93     **Objectives**

94     The primary objective of this pilot study will be to evaluate the safety, biological activity and  
95     pharmacodynamics of PTH 1-34 comparing delivery by twice daily subcutaneous injection vs. an insulin pump.  
96     The levels of serum calcium, phosphorus, magnesium, 1,25 OH vitamin D, bone markers, and mineral levels  
97     and cyclic AMP in the urine are the key physiologic responses to determine the adequacy of the PTH effect on  
98     hypoparathyroidism. We hypothesize that the delivery of PTH via pump therapy will maintain serum calcium  
99     in the normal range with minimal or no fluctuations in blood mineral levels. We anticipate that the small  
100     increments of PTH released by the pump will result in a normal physiologic pharmacodynamic profile of

serum calcium, magnesium, phosphorus and 1,25 vitamin D, normalize urine calcium and cause mild increases in urinary phosphorus and cAMP with no apparent peaks or troughs throughout the day.

This protocol is being conducted to study PTH delivered via pump vs. twice daily subcutaneous injections. PTH therapy via pump or twice-daily subcutaneous injections will be compared in a randomized crossover study consisting of two 3-month treatment arms.

The specific hypotheses and study endpoints are as follows:

We hypothesize that PTH pump therapy will be better tolerated, more convenient, and the preferred treatment modality. We expect that pump delivery of PTH will provide smoother metabolic control of serum and urine mineral levels compared to twice-daily injections. Our premise is that pump delivery will produce a more physiologic delivery of PTH by reducing brief episodes of hyper- and hypocalcemia throughout the day, will

permit improved calcemic control in the blood and will be more physiologic to the bone and kidney, with normal bone markers and reduced urine calcium.

The primary objective of this pilot study will be to evaluate the safety, efficacy, and pharmacodynamics of PTH1-34 given as twice-daily subcutaneous injection compared to an insulin pump. The levels of serum calcium, phosphorus, magnesium in the blood and urine are the key physiologic responses to determine the adequacy of the PTH effect on hypoparathyroidism. We hypothesize that the delivery of PTH via pump therapy will maintain serum calcium in the normal range with minimal or no fluctuations in blood mineral levels.

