We expect that occasional or no episodes of hypo or hypercalcemia will occur during both daily (pre-dose lab testing) or 24 h testing periods. Furthermore, there will be no diminishing effects of the pump's ability to maintain normal mineral homeostasis over the 3-month period.

Secondary objectives are:

Secondary objectives include measuring serum 1,25 OH vitamin D and cyclic AMP in the urine.

Biochemical marker of bone health: markers of bone formation and resorption in the blood and urine.

To determine if PTH therapy provides significant relief to patients with hypoparathyroidism who generally complain of debilitating fatigue, muscle weakness and decreased endurance. Fatigue scale questionnaire, a self measure of impact of fatigue (15) on activity and 6-minute walk-run test, a test of cardiovascular fitness and functional capability, in accordance with the guidelines and methods described and established by the American Thoracic Society (16,17). A biodex test of muscle endurance will also be performed. These tests will be administered in the Rehabilitation Medicine Department. These measures may help determine if PTH provides significant improvement of these symptoms. This section of the protocol will be performed by the Rehab Medicine collaborators.

**Study Design/Sample Size:** Study including 24 subjects with chronic hypoparathyroidism comparing PTH pump delivery vs twice daily PTH 1-34 injections.

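### The only power statement is for a rise in serum calcium 6 h after an injection, so the pump-versus-injection comparison of fluctuation has no defined endpoint and no stated precision

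*Combined protocol and SAP*

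**What the plan says.** **Sample size.** The Sample Size Justification paragraph, placed under Protocol Stopping Criteria, is the only power statement in the document supplied. Power was "based on the ability to observe a significant increase in serum levels of each outcome at the 6 h time point", a time chosen because that is "when PTH is known to peak after a subcutaneous injection". Calcium was used because "serum calcium levels exhibited the most variability and thus sample size calculations are based on this variable". The supporting data are from subcutaneous delivery: an "increase in serum calcium from 2.0 +/- 0.05 mmol/L at baseline to 2.3 +/- 0.10 mmol/L at 6 h". With an SD of 0.10 mmol/L and two-sided 0.05, 8 subjects are said to give 93% power for a rise of 0.10 mmol/L. Enrolment is 8 adults, then 16 children with more severe disease.

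**Hypothesis.** Objectives states a comparison between treatments: "We expect that pump delivery of PTH will provide smoother metabolic control of serum and urine mineral levels compared to twice-daily injections". The pump profile is anticipated "with no apparent peaks or troughs throughout the day".

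**Data.** Monitoring of Subjects says treatment responses at 3 and 6 months will be compared over 24 hours, with serum sampled two-hourly and urine four-hourly. It names no summary measure, contrast or model.

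**Outcome lists.** Objectives states the primary objective twice. The first statement is followed by a list of key responses that begins "The levels of serum calcium, phosphorus, magnesium, 1,25 OH vitamin D, bone markers, and mineral levels" and includes urinary cyclic AMP. The second names only calcium, phosphorus and magnesium in blood and urine. The secondary list then says "Secondary objectives include measuring serum 1,25 OH vitamin D and cyclic AMP in the urine" and adds bone markers.

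**The concern.** The sizing calculation and the hypothesis concern different quantities. A rise from baseline to the post-injection peak is a change within one regimen. Detecting it shows that an injection raises calcium, which the cited data already show. It does not show that the pump fluctuates less, and on the trial's own reasoning the pump should have no matching peak.

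The target also fits poorly as a statement about each outcome. Background and Scientific Justification reports that serum phosphorus stays elevated on PTH injections, so a further rise is not the benefit sought.

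Two things are at stake. A reader may take 93% as the power for pump versus injection, which it is not. And because smoothness is undefined, the 24-hour SD, the range, the share of values outside normal limits or the value at any one time could each be put forward after the profiles are seen.

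**Working it through.** **1. The plan's own figure.** Inputs from Sample Size Justification: n = 8, rise 0.10, SD 0.10, two-sided 0.05.

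- Paired t-test: effect/SD = 0.10/0.10 = 1; noncentrality 1 × √8 = 2.83 on 7 df. Power = 68%.
- Normal approximation: Φ(2.83 − 1.96) = Φ(0.87) = 81%.
- 93% appears only if the SD of the change is about 0.070. For example, SD 0.10 at both times with correlation 0.75 gives 0.10 × √(2 × 0.25) = 0.0707 and power 92.7%. The plan states no correlation.

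The mismatch in the inputs is a separate matter. Even if 93% were right, it would be power for a change within one regimen.

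**2. What the calculation contains and what the comparison needs.**

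| | Sample Size Justification | Pump versus injection |
|---|---|---|
| Contrast | 6 h minus baseline | Pump minus injection, same subject |
| Measure | Level at one time | Fluctuation over 24 h |
| Data | Subcutaneous only | Both treatments |
| Variance | SD 0.10 (level or change not stated) | SD of the within-subject difference (not given) |
| Period effect | None | Needed in a crossover |

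The cited rise is 2.3 − 2.0 = 0.30 mmol/L. With SD 0.10 and n = 8 it would be detected with power above 99.9%, using no pump data.

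**3. Precision for the comparison.** Let SD_d be the SD of the within-subject pump-minus-injection difference in the chosen measure, and δ the true difference. With equal sequence groups, no dropout and adjustment for period, the test has n − 2 df and noncentrality (δ/SD_d) × √n. Solving for δ/SD_d at two-sided 0.05:

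| n | 80% power | 90% power |
|---|---|---|
| 8 | 1.19 | 1.38 |
| 16 | 0.75 | 0.87 |
| 24 | 0.60 | 0.69 |

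Conversion to mmol/L needs SD_d, which the documents do not give. Purely as an assumed range, SD_d of 0.05 to 0.10 mmol/L would make the 80% detectable difference 1.19 × SD_d = 0.06 to 0.12 for n = 8, and 0.60 × SD_d = 0.03 to 0.06 for n = 24.

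**4. Illustration for a difference in calcium level, not in fluctuation.** Assume SD 0.10 in each period and correlation ρ between periods, so SD_d = 0.10 × √(2(1 − ρ)): 0.141 at ρ = 0 and 0.100 at ρ = 0.5. Power for a 0.10 mmol/L difference is 39% to 66% with n = 8, and 91% to over 99% with n = 24.

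**The case against.** - **It is a pilot.** Objectives says so, and the primary objective includes safety and pharmacodynamics. This lowers the need for high power. It does not make a calculation for another quantity informative about this one, and a defined contrast with a confidence interval suits a pilot well.
- **The comparison is planned.** Monitoring of Subjects does provide for a 24-hour comparison, and the profiles will be collected. This stands: the fault is in the definition and the stated precision, not in the design or the data.
- **The increase at 6 h could mean a difference between treatments.** The paragraph names no arm. But its data run from baseline to 6 h under subcutaneous delivery, and one time point would be at best a partial proxy for smoothness.
- **The choice of measure is partly judgement.** True. Objectives also speaks of episodes of hypo- and hypercalcemia, which could be counted. The need is for one measure chosen in advance, not for a particular one.
- **Earlier data may not help.** The documents mention previous data but do not show that two-hourly individual profiles exist. The Precis says the pump has not been used for PTH in this disease, so pump variance and the between-treatment correlation cannot come from earlier pump patients.

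**Conclusion.** The point stands as a mismatch between sizing rationale and hypothesis, joined to an undefined comparison. The 93% does not apply to pump versus injection, and nothing in the supplied text states the precision of that comparison. In standardised terms, the 80% detectable effect is about 1.2 SD_d with 8 subjects and 0.6 SD_d with 24. This assumes equal sequences, complete data and, for 24, that adults and children share one treatment difference and one variance.

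Three stronger readings are tempting but not supported:

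- *That the 6 h rise is the trial's decisive test, so it succeeds whatever the pump does.* The paragraph gives the basis for sizing; it does not declare the sole or primary analysis.
- *That the trial is too small.* Without an SD for any fluctuation measure, no corrected sample size or power can be computed. The level-difference illustration with 24 subjects is not unfavourable.
- *That testing each outcome inflates the error rate by a known amount.* No testing rule is set. For three serum minerals, independent and with all nulls true, the chance of at least one false positive would be 1 − 0.95³ = 14%. The plan itself reports a calcium rise, so the all-null premise does not hold for the 6 h tests.

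**What to change.** 1. Name one primary contrast: the within-subject pump-minus-injection difference in one pre-chosen measure of 24-hour serum calcium fluctuation, for example the SD of the two-hourly values, from the 3- and 6-month profiles. Leave out the pump-only day 7 profile, which has no injection counterpart.
2. Analyse it with a crossover model (treatment, period and sequence fixed; subject random) and report the estimate with a 95% confidence interval.
3. Stop presenting the 6 h rise and its 93% as the power for pump versus injection.
4. State precision in units of SD_d, as in the table above, for 8 adults, 16 children and all 24, and say whether pooling is intended. Convert to mmol/L with a sourced SD if earlier profiles are available; otherwise show an assumed range.
5. Make the other minerals, 1,25 vitamin D, cyclic AMP and bone markers secondary. Then the first list in Objectives agrees with the second, apart from the demoted minerals, and with the secondary objectives.

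The cost is protocol wording and a short precision calculation, with no new measurements. The downside is that phosphorus, magnesium and the urine minerals lose primary status.

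### The 93% power stated for 8 subjects cannot be obtained from the inputs given with it; a paired t test gives 68% if 0.10 mmol/L is the SD of the within-subject change

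*Combined protocol and SAP*

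**What the plan says.** The power statement is in the Sample Size Justification paragraph, under the heading Protocol Stopping Criteria of the combined protocol and SAP. It first sets the quantity being powered: "Our power estimates were based on the ability to observe a significant increase in serum levels of each outcome at the 6 h time point". Serum calcium is chosen as the most variable outcome. The earlier data cited for it show "an increase in serum calcium from 2.0 +/- 0.05 mmol/L at baseline to 2.3 +/- 0.10 mmol/L at 6 h". The calculation follows in one sentence: "With a standard deviation of 0.10 mmol/L, a two-sided significance level of 0.05 a sample size of 8 subjects will provide 93% power". The target of that calculation is a rise of 0.10 mmol/L in serum calcium.

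The next paragraph says that 8 adults will be enrolled first and 16 children with more severe disease afterwards. The total of 24 is repeated under Inclusion and Exclusion Criteria.

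The documents do not name the test, do not say whether 0.10 mmol/L is the SD of the change from baseline or the spread at one time point, and give no correlation between the baseline and 6 h values.

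**The concern.** The sentence gives four inputs and one output, so a reader should be able to recompute the output. The SD and the difference are both 0.10 mmol/L. Taken at face value this is a standardised effect of 1.0, and 8 subjects are too few for 93% power at a two-sided 5% level on that effect.

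This is the only power figure in the documents, and its 8 subjects match the first cohort of 8 adults. If the figure depends on an assumption that is not written down, nobody can judge whether the assumption is reasonable or how far the power falls when it is relaxed.

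**Working it through.** **Inputs**, all from the Sample Size Justification: n = 8; SD 0.10 mmol/L; two-sided alpha 0.05; difference 0.10 mmol/L; stated power 93%. The earlier data give 2.0 ± 0.05 at baseline and 2.3 ± 0.10 at 6 h. Reading ± as an SD is an assumption, but it matches the SD of 0.10 used in the power sentence.

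**Step 1. Try to reproduce 93% with 0.10 as the SD of change.** A rise from baseline in the same subject calls for a paired t test.

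- Noncentrality = difference / (SD of change / √n) = 0.10 / (0.10 / √8) = 2.83.
- Degrees of freedom 7, two-sided critical value 2.365.
- Power from the noncentral t distribution = 68.1%.

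Other tests on the same inputs:

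| Test, n = 8, SD 0.10, difference 0.10 | Power |
|---|---|
| Paired t, two-sided | 68.1% |
| Paired, normal approximation, two-sided | 80.7% |
| Paired t, one-sided | 81.5% |
| Paired, normal approximation, one-sided | 88.2% |
| 2×2 crossover t (df 6), 0.10 as SD of the difference | 65.7% |
| Two-sample t, 8 per group | 46.1% |

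None gives 93%. Using the root mean square of 0.05 and 0.10 as the SD of change gives 86.4%, which also misses.

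**Step 2. Take 0.10 as an SD at a time point.** The SD of change then depends on the correlation r:

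- SD of change = √(s₁² + s₂² − 2·r·s₁·s₂).
- Equal SDs of 0.10: √(0.02 × (1 − r)).
- SDs of 0.05 and 0.10: √(0.0125 − 0.01 × r).

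Paired t test, n = 8, two-sided 0.05, difference 0.10:

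| r | SD of change, 0.10/0.10 | Power | SD of change, 0.05/0.10 | Power |
|---|---|---|---|---|
| 0 | 0.141 | 41% | 0.112 | 59% |
| 0.25 | 0.122 | 51% | 0.100 | 68% |
| 0.5 | 0.100 | 68% | 0.087 | 80% |
| 0.75 | 0.071 | 93% | 0.071 | 93% |

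**Step 3. Solve for what 93% requires.**

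- Holding n = 8 and the difference at 0.10, the SD of change must be 0.0702 mmol/L. With equal SDs this is r = 1 − 0.0702² / 0.02 = 0.75. With SDs of 0.05 and 0.10 it is r = (0.0125 − 0.0702²) / 0.01 = 0.76.
- Holding n = 8 and the SD of change at 0.10, the difference must be about 0.142 mmol/L.
- Holding the difference and the SD of change at 0.10, n must be 14 (93.2%; n = 13 gives 91.1%).

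**Step 4. Full enrolment.** With 24 subjects, SD of change 0.10 and difference 0.10, paired power is 99.7%. This treats adults and children as one sample with a common SD.

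**The case against.** The strongest defence is that 0.10 was never meant as the SD of change. The only source shown for it is the spread at 6 h, a single time point. A correlation near 0.75 between two calcium values in the same subject is an ordinary repeated-measures assumption, and with it the paired t test gives 92.7%. The authors may have calculated correctly and left out one input. This stands. It means that 68% cannot be presented as the true power, and that an arithmetic slip is not established. It does not make the sentence verifiable, because the input that decides the answer is missing and power moves from 41% to 93% as it varies from 0 to 0.75.

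The defence can add that the planned difference is modest beside the earlier data, which show a rise of 2.3 − 2.0 = 0.30 mmol/L. For a rise of that size, 8 subjects have 99.9% power even with SDs of 0.10 at both times and no correlation. The study is also described as a pilot, and enrolment is 24. These points limit the consequence and stand as well.

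A reader might infer that the adults have a 32% chance of missing the target difference instead of 7%, and that a null adult result would therefore be over-read. The documents do not support this as a flat statement. The 32% holds only if 0.10 is the SD of change; across the table in Step 2 the chance of a miss runs from 59% to 7%. No decision rule in the documents turns on a null result for this contrast, and the earlier rise of 0.30 mmol/L makes one unlikely.

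**Conclusion.** The concern holds in conditional form: the stated 93% cannot be obtained from the stated inputs. Power at n = 8 for 0.10 mmol/L is 68% if 0.10 is the SD of the within-subject change. If 0.10 is a time-point SD, the answer is set by a correlation that the documents do not give, and 93% is reached only near 0.75.

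This rests on a paired t test for the rise from baseline to 6 h, on two-sided alpha 0.05 as stated, and on reading ± as an SD. It does not show that the trial is too small: with all 24 subjects pooled, a common SD and an SD of change of 0.10, power exceeds 99%. The defect is confined to the 8-subject power statement, which is wrong or incomplete as written.

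**What to change.** Rewrite the power sentence in the Sample Size Justification.

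1. Name the test (paired t) and say whether the SD is that of the within-subject change or that at one time point.
2. Check the earlier data for the SD of the change from baseline to 6 h. If they support a value near 0.070 mmol/L, state it, give its source, and show power across a range of correlations such as the table above.
3. Otherwise, replace 93% with 68% for a difference of 0.10 mmol/L, identify 0.10 as the assumed SD of change, and add that 8 subjects give 93% power for about 0.14 mmol/L.
4. If a figure for 24 subjects is quoted (over 99% with an SD of change of 0.10), say that it assumes adults and children are pooled with a common SD.

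The cost is one paragraph of wording and, for item 2, a look at data that the protocol already cites. Enrolment and procedures are unaffected. The downside is that, unless the smaller SD can be sourced, the stated power for the 8-subject calculation becomes less favourable.

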### Human Subjects Protections

*Risks and Discomforts:* The risks to the subjects are the pain of blood drawing and the risks associated with the bone biopsy as outlined below. Blood drawing by experienced personnel limits the risk of excessive pain, bruising and infection.

- (1) Pain associated with daily blood withdrawals and IV insertion.
- (2) Urine collections are an inconvenient but important part of the study.
- (3) Possible hypocalcemia or hypercalcemia: Participants in this study may experience symptoms of hypocalcemia or hypercalcemia before the proper dose of PTH is established. Patients who develop hypocalcemia will receive oral calcium supplementation until a sufficient dose of PTH is established. Severe hypocalcemia will be treated with intravenous calcium. Mild hypercalcemia will be treated by downward dose adjustment. For severe hypercalcemia, the patient will stop PTH therapy for at least one day and then resume treatment at a lower dose.
- (4) Development of resistance to PTH. These patients will show diminishing responsiveness to the therapy and will require increasingly greater doses of PTH to maintain normal serum calcium. Among the patients who develop resistance, many will be able to continue therapy if the resistance is small or partial. Others may develop substantial resistance with unstable serum calcium and phosphate levels. PTH therapy will have to be discontinued in these patients and calcitriol will be reinstituted.
- (5) Animal studies with rats with normal parathyroid function given up to seven times physiologic doses of PTH 1-34 daily from the time of weaning, for 18 months duration, demonstrated that some animals developed osteosarcomas. Although this experiment has little relevance to replacement therapy in humans, the remote possibility of bone cancer remains a risk factor.
- (6) Subjects may experience muscle soreness or pain during the muscle contraction test that is expected to quickly subside within minutes following the test.

*Potential Benefits:* Patients will likely receive direct benefit from their participation in the NIH study. They will be treated with the investigational drug PTH, which is not FDA approved for this disorder, but provides superior metabolic control. In addition, they will benefit from care by the principal investigator who is an expert in the care and monitoring of this rare disease.

*Confidentiality protection:* Several safeguards will be in place to protect the confidentiality of research findings. All data will be stored on computer that is password protected. Hard copies of forms will be identified by ID number only.

*Adverse Event Reporting:* All unanticipated new onset medical conditions will be reported to the IRB and FDA. Adverse events will be reported to the IRB and the FDA according to approved FDA and NIH guidelines.

